5. INDICATIONS OF EXPECTED RISKS AND BENEFITS FOR SUBJECTS IN THE STUDY

As no procedures or therapies are required there are no expected risks for patients participating to the registry. Despite no short-term benefits will be granted to any of participating patients, increasing knowledge of ES will bring to future benefits to the community, especially concerning the capacity to prevent recurrent shocks in ICD bearers.

Each subject will be informed both orally and by an appropriate document concerning procedures and purposes of the study. It will be clearly explained that participating (or not

participating) to the study will not change the frequency and type of clinical evaluations expected for the subject's disease. Patients can consult people they trust and they will have enough time to identify and ask any criticism and to gather further information; finally, patients will be asked to sign the informed consent if they agree to participate to the present registry. It will be stated that patient's participation to the registry is voluntary, free and that the consent can be withdrawn at any time and for any reason.

6. COSTS AND CONFLICT OF INTERESTS

The registry is cost-free as it does not require any further procedure or examination. The present protocol is promoted by the Marche Polytechnic University and it is not financed nor influenced by subjects with commercial interests in health. Participation in the trial by individual centers is free and voluntary and it will not interfere with clinical care activities.

Attachment #3- Case report form

 
Università Politecnica delle Marche - Clinica di Cardiologia Case Report Forms ELECTRA

Fill in following fields and "Enter"

0.1 - General Data
 
Last name  - First name  - Sex  - Birth date  Height (m)  - Weight (kg)  - NYHA 

0.2 - Risk factors and comorbidities
 
Hypertension  - Diabetes mellitus  - Previous Stroke or TIA  - Atrial Fibrillation  Previous episode of documented myocardial ischemia  - Peripheral artery disease 

0.3 - Chronic medical therapy (pre-storm)
 
Amiodarone  - Beta-blockers  - Ranolazine  Antiarrhythmic drugs class 1A  - Antiarrhythmic drugs class 1B  - Antiarrhythmic drugs class 1C  - Sotalol  - Digoxin 

0.4 - Laboratory exam
 
Haemoglobin (g/dl)  - Hematocrit (%)  - Creatinine (mg/dl)  - BNP (ng/dl)  - Kaliemia (mEq/l)  - Magnesemia (mEq/l) 

0.5 - Echocardiography (acute phase)
 
Ejection fraction (%)  - End-diastole interventricular septum (mm)  - End-sistole interventricular septum (mm)  Left ventricular diastolic diameter  - Left ventricular systolic diameter  - End-diastole posterior wall (mm)  - End-sistole posterior wall (mm) 

1.1 - ICD data
 
ICD type  - Implantation date  - Prevention  - Cardiomyopathy  ICD Brand  - ICD Model 


1.2 - Detection windows
 
VT detection rate  - VT if >24beats/12s  - ATP on VT  - Shock on VT  VT-1 detection rate (if present)  - VT-1 if >24beats/12s  - ATP on VT-1  - Shock on VT-1  VF detection rate  - VF if >24beats/12s  - ATP during charge 

2.1 - Electrical Storm
 
Electrical Storm geographical location  Electrical Storm start date  - Electrical Storm end date  - Electrical Storm beginning hour  Acute Coronary Syndrome as triggering ES event  - Acute Coronary Syndrome therapy  - ES triggering arrhythmias  Triggering arrhythmias cycle length  - Number of ATP delivered  - Number of shocks delivered  - Hospitalization length (days) 

2.2 - Previous arrhythmic events
 
Previous ES  - Previous VT/VF  - Previous VT ablation  - Previous inappropriate ICD therapies 

2.3 - ES medical management
 
Amiodarone  - Lidocaine  - Beta-blockers  - Sotalol  - Procainamide  Magnesium Sulfate  - Sedation  - Ablation  - CRT upgrade  - Pacing Overdrive  - Heart Transplant 

3.0 - ES ablation
 
Ablation date  - Ablation success  - Ablation number of attempts  - Ablation type  - Ventricular mapping  Endocardial approach  - Epicardial approach  - Electromechanical mapping  - Non contact mapping  - Irrigated tip catheters  Fluoroscopy time (min)  - Total procedure time (min) 


4.0 - Follow Up
 
Last follow-up date  - Vital status at last follow-up  - Number of total ES recurrences  - First ES recurrence date  Number of total VT/VF recurrences  - First VT/VF recurrence date  - Number of total HF rehospitalizations  - First HF rehospitalization date 

 

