2. AIM OF THE STUDY

The aim of the ELECTRA registry is twofold:

- a) To create an international registry on clinical features, optimal therapy, ablation strategy, prognosis and the effect of ICD programming on patients with ES.
- b) To use the data derived from the registry for a prospective, observational study on mortality and rehospitalization rate in patients with ES.

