4. OBSERVATIONAL STUDY DESIGN

Multicenter, observational, prospective clinical study. Data from the first 500 patients enrolled in the registry will be used for the present analysis. Please see point #3 of the present protocol for information regarding registry enrollment criteria and data collection.

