4.4 STATISTICAL ANALYSIS

The primary endpoint will be estimated annually and it will be expressed as absolute and relative numbers. Survival curves free from study endpoint, eventually divided into subgroups according to variables of interest such as gender, age, underlying heart disease, comorbidity and programming mode, will be drawn with Kaplan-Meier method and compared by Log-rank test. Basal and follow-up parameters (clinical, electrocardiographic and echocardiographic) will be compared by χ^2 test or by Fisher test if they are discrete; by T-student test or signed rank test if they are continuous. Every test will be two-tailed and a value of $p>0.05$ will be considered significant.

According to the number of centers involved we expect to recruit at least 500 patients. Considering an annual incidence of the primary endpoint (death from all causes) of 11% according to our experience (Guerra et al. Europace 2015), we expect about 55 events at the first statistical analysis after one year from the start and we expect about 165 events at the end of the follow-up of three years. The statistical analysis will be conducted using the SPSS 21.0 for Windows software (SPSS Inc. Chicago, IL, USA).

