Attachment #4 – Follow-up requested data for the observational study

- Last follow-up date
- Vital status (alive, sudden cardiac death, non-sudden cardiac death, non-cardiac death, dead for unknown reasons)
- Total number of electrical storm recurrences
- First electrical storm recurrence date
- Total number of unclustered ventricular arrhythmia recurrences
- First unclustered ventricular arrhythmia recurrence date
- Total number of rehospitalization for heart failure
- First rehospitalization for heart failure

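### CRT upgrade and heart transplant are recorded without dates and later transplant has no follow-up field, so any survival comparison by treatment made with the stated method would favour the treated group

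*Combined protocol and SAP*

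**What the plan says.** **Aims and endpoint.** Section 2, aim (a), is a registry on "clinical features, optimal therapy, ablation strategy, prognosis and the effect of ICD programming on patients with ES". Aim (b) uses the same data for a study of mortality and rehospitalization. Section 4.1 counts all-cause mortality over 3 years from the ES.

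**Method.** Section 4.4 plans "Survival curves free from study endpoint, eventually divided into subgroups according to variables of interest", drawn by Kaplan-Meier and compared by log-rank. The examples given are gender, age, underlying heart disease, comorbidity and programming mode. They are introduced as examples, so the list is open, but no treatment is among them. The plan has no regression model, time-dependent variable or landmark. Section 3.3 places ES management under descriptive analysis.

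**Data capture.** In Attachment #3, "2.3 - ES medical management" gives ablation, CRT upgrade and heart transplant one selection box each, beside the acute drugs. CRF 3.0 adds a single ablation date and a count of attempts. CRF 4.0 and Attachment #4 collect vital status, ES and VT/VF recurrences and heart failure rehospitalizations. The vital status options in Attachment #4 are "alive, sudden cardiac death, non-sudden cardiac death, non-cardiac death, dead for unknown reasons". Section 4.3 asks centres to report every new admission with its cause.

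**The concern.** A patient can be ablated, upgraded or transplanted only while alive. If patients are sorted at the ES by a treatment that comes later, those who die before they could receive it fall into the untreated group. The treated group is then credited with time in which its members could not have died. This favours treatment even when it does nothing, and it applies to prospectively enrolled patients as much as to retrospective ones.

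For CRT upgrade and transplant the form holds no date, so an analyst could not correct for this from the form.

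Relapse data have a related gap. A patient transplanted during follow-up is entered as alive, and later months without ES or VT/VF count as relapse-free although the heart that produced the storm has been replaced. A relapse analysis that ignored this would flatter the management given before transplant.

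**Working it through.** **1. The plan's own figures.** Section 4.4 assumes 11% annual mortality in 500 patients. 500 × 0.11 = 55 agrees with "we expect about 55 events at the first statistical analysis after one year from the start", and 500 × 0.11 × 3 = 165 agrees with "we expect about 165 events at the end of the follow-up of three years". These are linear products. Compounding gives 500 × (1 − 0.89³) = 147.5 deaths at 3 years. The steps below use the compounded form.

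**2. Assumptions.** The documents give neither the share treated nor the delay from ES to treatment. Assumed: 20% or 40% are destined for treatment at a time uniform over 0 to D months, and are treated only if still alive then. Treatment has no effect. Follow-up is 3 years from the ES.

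**3. Worked case, D = 12 months, constant hazard.**
- Hazard λ = −ln(0.89) = 0.11653 per year. Three-year survival is 0.89³ = 0.70497, so deaths per patient are 0.29503 and person-years are 0.29503 / 0.11653 = 2.53171.
- Per destined patient, the chance of living to treatment averages (1 − 0.89) / 0.11653 = 0.94393. Deaths after treatment are 0.94393 − 0.70497 = 0.23896.
- Person-years credited to the treated group per destined patient: before treatment, ∫₀¹ w·e^(−λw) dw = 0.46280; after treatment, 0.23896 / 0.11653 = 2.05059; total 2.51339.
- Treated rate: 0.23896 / 2.51339 = 0.09508.
- Untreated rate, 20% destined: (0.29503 − 0.2 × 0.23896) / (2.53171 − 0.2 × 2.51339) = 0.24724 / 2.02903 = 0.12185. Ratio 0.78.
- Untreated rate, 40% destined: (0.29503 − 0.4 × 0.23896) / (2.53171 − 0.4 × 2.51339) = 0.19945 / 1.52635 = 0.13067. Ratio 0.73.

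**4. Simulation across delays.** Ratios come from 1,000,000 patients per scenario. False-positive rates come from 3,000 simulated studies of 500 patients, two-sided log-rank at 0.05. Each cell gives 20% / 40% treated. The last column triples the hazard in the first 3 months with 3-year mortality unchanged (a further assumption).

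| Delay (months) | Ratio, constant hazard | Log-rank false positives, constant hazard | Ratio, tripled early hazard |
|---|---|---|---|
| 0-1 | 0.982 / 0.979 | 5% / 5% | 0.942 / 0.919 |
| 0-3 | 0.939 / 0.923 | 5% / 8% | 0.835 / 0.785 |
| 0-6 | 0.889 / 0.852 | 7% / 15% | 0.725 / 0.671 |
| 0-12 | 0.778 / 0.724 | 19% / 44% | 0.625 / 0.557 |

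The 12-month row agrees with step 3 to within 0.005.

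**5. Does reallocating time remove the bias?** At constant hazard, moving time before treatment to the untreated group returns the ratio to 0.99-1.01. With the tripled early hazard, a crude person-time split is not enough: for delays up to 12 months the ratio stays at 0.76-0.96, because the untreated group keeps most of the high-risk early months. The comparison must be between patients at the same time since the ES. Counting a patient as treated only from the treatment time, and comparing observed with expected deaths at each death time (ratio = exp[(O − E)/V]), I obtained ratios within 0.01 of 1 in the tripled-hazard scenarios. A Cox model with a time-dependent treatment variable makes this kind of comparison.

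**The case against.** The strongest reply is that the plan contains no such analysis. A reader might infer that treated patients will be credited with earlier survival and that ablation will therefore look protective. The documents do not support that as fact: no treatment is a named subgroup, Section 4.4 serves aim (b), and Section 3.3 puts ES management under description. This stands, so the bias is conditional. What remains is that aim (a) includes prognosis beside therapy, the subgroup list is open, and no other survival method is offered.

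A reader might also take the boxes in CRF 2.3 as ever/never items. The options are not shown, and the heading may confine them to the index episode, where delays and bias would be small. The form does not say so, and centres could answer differently.

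It is tempting to call transplant invisible at follow-up. That goes too far: it has a box in CRF 2.3, and a later transplant admission should be reported with its cause under Section 4.3. What is missing is a field and a date.

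For ablation, the recorded date and the ES start date already permit a time-dependent or landmark analysis of one dated procedure. The plan does not ask for it, and a single date cannot describe several attempts.

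Finally, no relapse-free survival analysis is specified. The relapse point therefore concerns data that are collected and named in the heading of Section 4.3, not an endpoint.

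**Conclusion.** The gaps in data capture are plain from the forms: no date for CRT upgrade or transplant, one date for possibly several ablations, no time window for CRF 2.3, and no transplant field in CRF 4.0 or Attachment #4. The bias in survival comparisons follows only if survival is compared by a treatment given after the ES with the one method stated.

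Its size depends on delay and share treated, both assumed here. At constant hazard it is negligible when treatment comes within about a month, modest within three, and large enough to mislead when treatment is spread over a year. A higher early hazard, also assumed, would enlarge it at every delay. Only a treatment such as ablation, with an assumed share of 20-40%, is represented; nothing has been quantified for CRT upgrade or transplant specifically.

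All-cause mortality and all-cause hospitalization, as defined, are not affected. This is a cheap improvement worth making while the dates can still be collected, not a fault in the main analysis.

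**What to change.** 1. **CRF and Attachment #4.** State the time window that CRF 2.3 covers. Add dates for CRT upgrade, heart transplant and each ablation. Add a yes/no item with date for heart transplant to CRF 4.0 and Attachment #4.
2. **Section 4.4, treatment comparisons.** State that any survival comparison by a treatment given after the ES will use a time-dependent treatment variable, or start at a fixed landmark among patients alive then, grouped by treatment received up to that point.
3. **Section 4.4, transplant.** State how transplant is handled in any ES or VT/VF relapse analysis, for example as censoring or as a competing event. Keep all-cause mortality as the primary endpoint.

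The cost is a few form fields and a few sentences. A landmark drops earlier deaths from that comparison only. A time-dependent analysis needs a Cox model, which the named software provides. No additional patient procedure is involved.

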Attachment #4 – Follow-up requested data for the observational study

- Last follow-up date
- Vital status (alive, sudden cardiac death, non-sudden cardiac death, non-cardiac death, dead for unknown reasons)
- Total number of electrical storm recurrences
- First electrical storm recurrence date
- Total number of unclustered ventricular arrhythmia recurrences
- First unclustered ventricular arrhythmia recurrence date
- Total number of rehospitalization for heart failure
- First rehospitalization for heart failure

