4.1 PRIMARY ENDPOINT

- All-cause mortality 3 years after the ES

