4.3 ANALYSIS OF RELAPSES AND MORTALITY

Each center will be asked to report every new hospital admission of patients enrolled in the study and the cause of hospitalization. Moreover, data about subjects' vital status will be asked to be updated every 6 months.

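### No form asks for the date of death, so the timing of the primary endpoint depends on an undefined last follow-up date that may fall up to about 6 months after the death

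*Combined protocol and SAP*

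**What the plan says.** Section 4.1 sets the primary endpoint as "All-cause mortality 3 years after the ES". Section 4.4 uses it in two ways. First: "The primary endpoint will be estimated annually and it will be expressed as absolute and relative numbers". Second, survival curves, optionally split by subgroup, "will be drawn with Kaplan-Meier method and compared by Log-rank test".

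The time origin is available, because CRF section 2.1 (Attachment #3) has a field "Electrical Storm start date". At the other end, CRF section 4.0 offers "Last follow-up date" and "Vital status at last follow-up". Attachment #4 repeats the follow-up date and asks for "Vital status (alive, sudden cardiac death, non-sudden cardiac death, non-cardiac death, dead for unknown reasons". No section of the CRF and no item in Attachment #4 asks for a date of death.

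Other events do have dates. CRF section 4.0 has separate date fields for the first ES recurrence, the first VT/VF recurrence and the first heart failure rehospitalization. Attachment #4 dates the first two of these but asks for no date for the third.

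On frequency, section 4.3 says that data on "vital status will be asked to be updated every 6 months". It does not say that the day of death should be reported.

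**The concern.** A Kaplan-Meier curve, a log-rank test and an annual count all need each death placed in time. For a patient who has died, the single available date could be one of three things: the day of death, the contact at which the centre learned of it, or the last visit alive. No text chooses among them.

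The CRF wording points to the second, since a status as at the last follow-up that is a death can only have been established on or after the day of death. With 6-monthly updates, that contact can come up to about 6 months later. Deaths would then enter the curve too late, and annual mortality would be understated. The entered value does not show which meaning a centre used, so the analyst could not correct it from the database.

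**Working it through.** **Inputs.** From section 4.4: 500 patients and 11% annual mortality. From section 4.3: an update interval of 6 months. Assumed, because the documents are silent: constant hazard, and contacts at a random phase relative to the ES.

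**The plan's own figures.** 500 × 0.11 = 55 deaths at 1 year and 500 × 0.11 × 3 = 165 at 3 years; both match section 4.4. With the risk set shrinking as patients die, the 3-year figure is 500 × (1 − 0.89³) = 147.5, or 29.5%. The point made here does not depend on that difference. I use 11.0% at 1 year and 29.5% at 3 years as the true values.

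**Deaths dated at the next contact.** Such a death is counted by year *a* only if it occurred before the last contact at or before *a*. That contact lies *u* years before *a*, with *u* uniform on 0 to 0.5. With λ = −ln 0.89 = 0.1165 per year, averaging over *u* gives

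reading = 1 − 0.89^a × (e^(0.5λ) − 1)/(0.5λ) = 1 − 0.89^a × 1.0297.

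- 1 year: 1 − 0.89 × 1.0297 = 8.4% (about 42 deaths instead of 55). Bias −2.6 points.
- 3 years: 1 − 0.7050 × 1.0297 = 27.4% (about 137 deaths instead of 147.5). Bias −2.1 points.

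The mean delay is 3 months.

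**Sampling error for comparison (95% half-width, n = 500).**

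- 1 year: 1.96 × √(0.11 × 0.89/500) = 2.7 points.
- 3 years: 1.96 × √(0.295 × 0.705/500) = 4.0 points.

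**Deaths dated at the last contact alive.** The factor becomes (1 − e^(−0.5λ))/(0.5λ) = 0.9714.

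- 1 year: 1 − 0.89 × 0.9714 = 13.5% (simulation gave 13.6%).
- 3 years: 1 − 0.7050 × 0.9714 = 31.5%.

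**Conditions under which the bias vanishes.**

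- If every centre enters the day of death, the shift is zero.
- If contacts fall at exactly 6, 12, … 36 months after the ES, a death before an annual cut-off has its next contact no later than that cut-off, and a death after it has its next contact later still. Late dating then leaves the annual figures at 11.0% and 29.5%, although deaths still move within the curve.

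**Group comparisons.** I simulated two groups of 250 with identical true survival over 3 years. The log-rank test rejected in about 5% of runs with true dates. It rejected in roughly 9 to 11% when one group carried contact dates and the other true dates, and in roughly 20 to 23% when one group was dated late and the other early. These are worst cases in which dating habit coincides completely with group. When both groups were dated late, rejection stayed at about 5%.

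**The case against.** The best defence is that a last follow-up date paired with a status is a usable time-and-status record, and that many centres will enter the day of death without being told to. Some probably will. Nothing on the forms or in section 4.3 tells them to, so this is a hope rather than a safeguard.

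A second defence is that the primary endpoint is largely a count at 3 years, which depends on vital status at the cut-off more than on exact dates. That is fair, and it is why the 3-year bias is smaller relative to its sampling error than the 1-year bias. But section 4.4 also plans annual estimates and survival curves, and those depend on the dates.

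Several stronger readings are tempting but not supported:

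- **That the error is as large as the study's sampling error at 3 years.** A reader might set the 4.1-point gap between the early and late extremes (31.5% − 27.4%) against the 4.0-point half-width. That compares a full spread with half an interval. The error in one direction is about 2 points, and an even mix of early and late dating would largely cancel in the overall estimate.
- **That early dating is as likely as late dating.** Entering the last visit alive contradicts the CRF label. The 31.5% also arises only by moving deaths after year 3 back across the cut-off; counting only deaths that occurred within 3 years, early dating leaves the figure at 29.5%.
- **That differences between centres bias the subgroup comparisons.** Programming mode could vary by centre, but no text shows that dating habits line up with any group compared. This is a possibility only.
- **That the dates are lost for good.** Section 3.2 has local investigators or their delegates keep the code list, so centres can be asked.

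**Conclusion.** The point holds at a moderate size. The forms never ask for the date of the primary event, and the one date tied to vital status is undefined for patients who have died. Under the literal reading of the CRF, the estimate could be too low by up to 2.6 points at 1 year, about as large as the sampling half-width there, and by up to 2.1 points at 3 years, about half the half-width. If centres instead entered the last contact alive, the readings could rise to about 13.5% and 31.5%.

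These figures assume 11% annual mortality at a constant hazard, contacts at a random phase, and every death misdated in the same direction. They are upper illustrations, not a forecast. Distortion of subgroup curves would occur only to the extent that dating habits align with the groups compared. I class this as a cheap improvement.

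**What to change.** 1. Add a date-of-death field to CRF section 4.0 and to Attachment #4.
2. Define the last follow-up date as the date last known alive, for patients not known to be dead.
3. State in section 4.4 that deaths are timed at the date of death and that all other patients are censored at the date last known alive.
4. Query centres for the dates of deaths already entered.

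The cost is one extra date on two forms, two sentences of text and a short query to centres. No patient procedure is added.

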3. REGISTRY DESIGN

The creation of the present registry is aimed at gathering information on a wide cohort of patients affected by ES. All patients will be enrolled for a minimum of three years from the protocol approval. There is no pre-specified date for the end of enrollment, which will be decided by the study responsible according to the enrollment rate.

A minimum of 500 patients will be included in the present registry. The exploratory nature intrinsic to the registry characteristics does not allow a sample size calculation by statistical means. However, the sample presented is based on the estimated enrolment rates of the participating centers during a 3-year enrolment period. Moreover, the sample size is large enough to postulate specific subgroup analyses.

REGISTRY INCLUSION CRITERIA:

- Diagnosis of ES (documentation of 3 or more episodes of sustained ventricular arrhythmia within 24h or documentation of sustained ventricular tachycardia lasted at least 12h). In order to fulfill this criterion, a patient with a previous episode of ES could also be enrolled during routine screening.
- Age ≥ 18
- Written informed consent

REGISTRY EXCLUSION CRITERIA:

- patient without ICD
- Confirmed or suspected use of drugs or narcotics with known direct pro-arrhythmic effect
- Inability to express an informed consent for the study

At enrollment, each patient will be informed on the aim and the design of the study, and the investigations needed. All patients that meet the inclusion criteria will be included in the study (attachment #1). All recruited patients will receive the informative form (attachment #1) and the informative letter to their general practitioner (attachment #2).

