3.2 DATA COLLECTION

No additional procedures are required to the participating centers. Data usually collected in the center and necessary for the analysis will be collected by the referent investigator. Considering that ICDs record the principal events of the whole life of the device, patients with an ES previous to the creation of this registry will be included retrospectively providing that:

- 1) clinical data from the participating center are complete and accurate and allow to check inclusion and exclusion criteria
- 2) follow-up is available
- 3) ICD has not been replaced, leading to the loss of original data
- 4) ECG and echocardiography done in routine practice are available in case of necessity
- 5) subject agrees to subscribe the informed consent during the next routine visit in the recruiting center

All data will be used with scientific research purposes only. Data will be saved on a dedicated website⁷ in agreement with current regulations on the treatment of personal data. Electronic cards of data collection transmitted to the study responsible will be identified by an alphanumeric code. The list of matches between subjects' data and these codes will be created and kept by local investigators or delegates. The data manager is the study responsible.

For the type of data requested, see Case Report Form (attachment #3)

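### Patients enrolled after an earlier electrical storm must survive to consent, yet the plan gives no delayed-entry rule for endpoints timed from the storm

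*Combined protocol and SAP*

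**What the plan says.** Sections 4.1 and 4.2 define the endpoints as all-cause mortality and all-cause hospitalization three years after the ES, so time zero is the storm.

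Enrolment is not confined to new storms. Section 3 states that "a patient with a previous episode of ES could also be enrolled during routine screening". Section 3.2 adds that "patients with an ES previous to the creation of this registry will be included retrospectively", on several conditions, among them that the "subject agrees to subscribe the informed consent during the next routine visit in the recruiting center". Section 4 calls the study prospective and says: "Data from the first 500 patients enrolled in the registry will be used for the present analysis". It does not cap or separate the past-storm patients.

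On analysis, section 4.4 says: "The primary endpoint will be estimated annually and it will be expressed as absolute and relative numbers". Survival curves "will be drawn with Kaplan-Meier method and compared by Log-rank test". It has no entry date for patients enrolled after an earlier storm. Section 4.3 says data on "vital status will be asked to be updated every 6 months". Attachment #4 lists the item as "Vital status (alive, sudden cardiac death, non-sudden cardiac death, non-cardiac death, dead for unknown reasons". Neither Attachment #4 nor the case report form (Attachment #3) shows a date of consent.

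**The concern.** A past-storm patient is in the dataset only because he or she was alive to sign the form. The time from storm to signature is therefore free of deaths by selection. An ordinary Kaplan-Meier curve started at the storm treats that time as if the patient had been at risk and survived. A simple percentage of the 500 has the same fault. Both make three-year mortality look too low, and mortality is what the study sets out to estimate.

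The subgroup comparisons are exposed as well. If the past-storm share or the delay differs between the groups compared, for example by programming mode, the log-rank test can show a difference that comes only from how the patients were enrolled.

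**Working it through.** **The plan's own figure.** 500 x 0.11 = 55 deaths in one year, and 3 x 55 = 165 in three. This reproduces section 4.4, as a straight count that leaves the dead in the denominator. A survival curve removes them:
- 11% as a rate: 1 - exp(-0.33) = 28.1%, or 141 of 500.
- 11% as a yearly risk: 1 - 0.89^3 = 29.5%, or 148 of 500 (rate 0.1165).

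**Inputs.** From section 4.4: h = 0.11 a year and N = 500. From section 4.1: three years. Assumed, because the plan gives no figure: a share f of the 500 consents L years after the storm, and the rest are followed from the storm. The hazard is taken as constant.

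**Counted from the storm.** Apparent mortality = 1 - [(1 - f) x exp(-hL) + f] x exp(-h(3 - L)). The lone f is the group whose survival to L is certain.

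Example, f = 0.5 and L = 2: [0.5 x 0.8025 + 0.5] x 0.8958 = 0.9013 x 0.8958 = 0.807, so apparent mortality is 19.3%.

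| f | L (years) | Apparent (true 28.1%) | Relative error | Deaths seen |
|---|---|---|---|---|
| 0.1 | 0.25 | 27.9% | -0.7% | 140 |
| 0.2 | 0.5 | 27.3% | -2.9% | 136 |
| 0.2 | 1 | 26.4% | -5.9% | 132 |
| 0.2 | 2 | 24.6% | -12.6% | 123 |
| 0.5 | 1 | 23.9% | -14.9% | 120 |
| 0.5 | 2 | 19.3% | -31.5% | 96 |

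With rate 0.1165 (true 29.5%) the last four rows become 27.8%, 25.8%, 25.1% and 20.3%.

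**Effect on a comparison.** Two subgroups with the same true mortality, one as in row 3 and one as in row 6, would appear as 26.4% and 19.3%, a gap of 7.1 points.

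**With entry at consent.** The hazard at each time since the storm is then estimated only from patients under observation. It is 0.11 throughout, so the expected estimate is 28.1%. Simulation over the four rows with L of 1 or 2 years gave 28.0-28.2%.

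**Price in precision** (Greenwood form). Variance = exp(-6h) x [(exp(hL) - 1)/n1 + (exp(h(3 - L)) - 1)/n2], where n1 is the number at risk from the storm and n2 the number at risk just after L.
- No late consent: 0.5169 x 0.3910/500 = 0.000404, standard error 2.0 points.
- f = 0.5, L = 2: n1 = 250 and n2 = 250 x 0.8025 + 250 = 450.6. Then 0.5169 x (0.2461/250 + 0.1163/450.6) = 0.000642, standard error 2.5 points.
- f = 0.7 or 0.8, L = 2: 3.1 or 3.7 points.

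**The case against.** The best case for the plan is that the bias may be trivial. Section 3.2 places consent at the next routine visit. If few patients are affected and the delay is a few months, the error is about 1-3% in relative terms, well inside sampling error. Section 4.4 also does not forbid delayed entry, and section 3 calls the registry exploratory.

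Part of this stands. The size is unknown and could be small. But the next routine visit is next for the registry, not next after the storm. Section 3.2 speaks of storms that predate the registry, so the delay from storm to consent can be much longer than one visit interval. Being exploratory excuses the lack of a hypothesis, not an undefined risk set for the primary endpoint.

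A reader might go further and infer that the plan is at fault for collecting cause of death without analysing it. The documents do not support that. Aim (b) is mortality and rehospitalization, which all-cause endpoints fit. Other Attachment #4 items, such as storm recurrences and heart failure readmissions, also have no named estimate. The report list in section 3.3 is not closed, and the generic comparison of clinical follow-up parameters in section 4.4 could take in the death class, although it names no sudden-death estimate.

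**Conclusion.** The concern holds for the entry rule. With the clock started at the storm and no delayed entry, three-year mortality is understated whenever past-storm patients are included. The error ranges from under 1% (10% of patients, three months) to 31.5% (50% of patients, two years) in relative terms. That range rests on a constant hazard of 0.11 and on assumed shares and delays. The documents do not show where ELECTRA falls in it, so it would be wrong to say that the primary result is known to be badly biased.

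Two limits apply. The arithmetic covers death only; the effect on hospitalization is not sized here. Nor does the relative error carry over to each cause of death unless the mix of causes is constant over time since the storm; if sudden deaths cluster early, they would be understated more than the rest.

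The rule should be settled before the analysis. It does not call the choice of endpoints into question.

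**What to change.** Add to section 4.4:

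> Time runs from the ES. A patient enrolled after an earlier ES enters the risk set on the date of written consent. This applies to the Kaplan-Meier curves and log-rank tests for all-cause death and to the analysis of all-cause hospitalization; a patient already readmitted before consent is not at risk of a first readmission. Annual deaths are reported as counts, and the percentage is the Kaplan-Meier estimate.

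Add the consent date to the case report form. Sites can copy it from the written consent that section 3 already requires. No visit or procedure is added.

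Costs:
- Time before consent is lost, and patients who consent more than three years after the storm contribute nothing.
- The standard error rises from 2.0 to about 2.5 points with half the patients two years late, and further if the past-storm share is larger.
- Software other than the package named in section 4.4 may be needed.
- Delayed entry assumes that the delay to consent is unrelated to later risk. The report should say so.

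Optional: since cause of death is already requested, a descriptive Aalen-Johansen cumulative incidence by cause could be added under the same entry rule, with unknown causes counted as sudden in a sensitivity analysis. All-cause mortality stays primary.
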